## **8.2 Implementation of the Learning and Validation steps**

It is important to note that during the Validation phase of the project, [name] PhD, MBA will be excluded from evaluating the performance of the VPG technology because of the potential for a conflict of interest. His role during this phase of the project will be that of a technical consultant only. In addition, for the validation phase, blinded study data will be sent to RIT for processing and the results will be sent to [name] (U of R) for evaluating the performance of the tested technology to detect the presence of AF. [name], Department of Biostatistics, will be responsible for the statistical analysis of the clinical data at the UR.

**-AIM1, Detection Performance of VPG:** To address Aim 1 we will use the Training Data) to construct a classifier to predict AF as a function of facial VPG measures, then we will use the Validation Data to provide an unbiased characterization of its performance on independent subjects. Each subject will record a baseline VPG during sinus rhythm. During the 2-week follow-up period, subjects will be asked to record a video selfie (VPG) twice per day, each synchronized with the ECG recording from the Zio patch. Subjects will be asked to perform additional VPG recordings any time they feel symptomatic. The longitudinal binary outcome at each follow-up time will be AF as determined by ECG. We expect to have a minimum of 29 outcomes per patient (2 weeks x 7 days/week x 2 recordings/day + 1 baseline) x 142 patients (half of the 315 enrolled x 90% converted) = 4K outcomes in the Training Data (and similarly in the Validation Data), each with an associated VPG from which the 8 VPG measures described above (PR, heart rate, RMSSD, SDRR, pNN50, SD1, SD2, AFEvidence) will be calculated.

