We will also construct ROC curves based on the Validation Data to display the trade-off between sensitivity and specificity as a function of the threshold for the linear predictor, and we will compare these to cross-validation-based (as well as optimistic naïve) ROC curves based on the Training Data. To investigate calibration, we will fit a marginal logistic model to the Validation Data with the un-thresholded linear predictor as the sole predictor. Testing the null hypothesis that the slope in this model is 0 tests whether the model is useless, and thus we hope and expect to strongly reject this null hypothesis with a tiny p-value; testing the null hypothesis that the slope is 1 is a test of calibration, and we hope that we fail to reject this null hypothesis with a large p-value (indicating good calibration). We will also use the Validation Data to re-estimate all of the individual coefficients in the marginal logistic regression model, for comparison with the potentially biased estimates from the Training Data.

**-AIM2: Benefit of using Baseline VPG Recording:** Each subject will have a baseline VPG recorded during sinus rhythm (using the Samsung Tablet). This recording will be acquired after successful procedure and before the subject leaves the hospital. Sinus rhythm will be checked by health professional. To address Aim 2, we will repeat the above general procedure but based on the *differences* from baseline in VPG measures and/or by including the baseline VPG measures along with the instantaneous VPG measures for predicting AF at each time point. When the time comes to open the Validation Data, we will compare the sensitivity and specificity of the classifier from Aim 2 to that of Aim 1 to quantify the potential improvement due to incorporating a baseline VPG.

[figure not shown]

Figure 7: Schematic presentation illustrating the true and false detection of AF and SR rhythm during the 14-day follow-up period of the study. The upper line represents the continuous ECG recording (either blue or black for SR and AF, respectively), while the lower line presents the same 14-day period during which VPG will be recorded. The VPG monitoring periods in which 5 recording sessions are marked (limited to 5 for clarity purpose). We will have at least 2 recording sessions per day, i.e., 28 recordings sessions.

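### The only calibration test, slope = 1 with a free intercept, cannot detect AF probabilities that are uniformly too high or too low, and a large p-value is taken as good calibration

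*Combined protocol and SAP*

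**What the plan says.** The calibration plan is in section 8.2, AIM1, after the ROC curves: "To investigate calibration, we will fit a marginal logistic model to the Validation Data with the un-thresholded linear predictor as the sole predictor". Two tests are taken from this model.

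- Slope = 0: "Testing the null hypothesis that the slope in this model is 0 tests whether the model is useless". This is a test of association.
- Slope = 1: "testing the null hypothesis that the slope is 1 is a test of calibration, and we hope that we fail to reject". The hoped-for result is to "fail to reject this null hypothesis with a large p-value (indicating good calibration").

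The plan gives no test or interval for the intercept, no comparison of mean predicted with observed AF, no calibration plot, and no margin or interval criterion for the slope. No significance level is stated for the slope test.

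One further step is related. The Validation Data will be used to "re-estimate all of the individual coefficients in the marginal logistic regression model, for comparison with the potentially biased estimates from the Training Data". No criterion is attached to that comparison.

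**The concern.** Calibration has two basic parts. The level part asks whether predicted AF probabilities are right on average. The spread part asks whether they are too extreme or not extreme enough. The slope addresses only the spread. If the intercept is free, it absorbs any error in level, and the slope test is unaffected.

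The second problem is that a non-significant test of slope = 1 is treated as positive evidence. Non-rejection can also reflect an imprecise slope estimate, and the plan sets no precision or margin.

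At stake is the calibration statement that the study would publish. A classifier whose AF probabilities are uniformly too high or too low could be reported as well calibrated. The documents do not show that such a shift will occur. However, under section 3.1.1 the learning and validation sets come from successive 17.5-month enrolment periods rather than a random split, so equal AF frequency in the two sets is not guaranteed by design.

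**Working it through.** The documents give no calibration figure, so there is none to reproduce. The check has three steps.

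**1. Invariance (algebra, no assumption about the data)**

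The model is logit P(AF) = a + b·LP, where LP is the linear predictor. The text does not mention the intercept a. A free intercept is the default for a logistic model with one predictor, and nothing in the text constrains it.

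Replace LP by LP + c:

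- Setting a′ = a − b·c and b′ = b gives the same fitted probabilities.
- The score equations Σ(y − p) = 0 and ΣLP·(y − p) = 0 imply Σ(LP + c)·(y − p) = 0, so (a′, b) is the new solution.
- The new design matrix is the old one times A = [[1, c], [0, 1]], so the sandwich covariance becomes A⁻¹V(A⁻¹)ᵀ. The second row of A⁻¹ is (0, 1), so the variance of b does not change.

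The p-value for b = 1 is therefore the same for every c. A numerical check on one simulated data set of 142 × 29 = 4,118 observations, with observed AF of 13.2%, gave:

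| Constant added to LP | Mean predicted AF | Slope | Robust SE | p for slope = 1 |
|---|---|---|---|---|
| 0 | 13.1% | 1.068 | 0.042 | 0.105 |
| +1 | 22.7% | 1.068 | 0.042 | 0.105 |
| −1 | 6.8% | 1.068 | 0.042 | 0.105 |
| +2 | 35.5% | 1.068 | 0.042 | 0.105 |

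All four sets of predictions would receive the same calibration verdict.

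**2. Size of what could be missed (simulation)**

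Inputs from the documents:

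- 142 validation patients with 29 recordings each (section 8.2: "We expect to have a minimum of 29 outcomes per patient")
- 35% or 65% of patients ever in AF (section 8.1)
- sensitivity and specificity of 85%, the value assumed in section 8.1

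Inputs assumed, because the documents do not give them:

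- LP normal with equal variance in each rhythm
- one AF episode per AF patient, with mean length 15% or 35% of the 28 follow-up recordings
- subject-level variance share of 0 or 0.4
- two-sided 5% tests with subject-clustered standard errors

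This gives 8 scenarios, each with 1,000 simulated data sets. AF prevalence was 6–22% of recordings.

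Every predicted odds was doubled, so the true calibration intercept is −ln 2 = −0.69.

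- Slope = 1 was not rejected in 91–95% of data sets. The rate was identical to that for the unshifted data in every scenario, and the largest change in the slope estimate was 3 × 10⁻¹⁵.
- Mean predicted against observed AF was 8.6% against 5.8% in the lowest-prevalence scenario and 27.9% against 21.7% in the highest.
- The intercept test (LP as offset, slope fixed at 1) rejected in 91–100% of the same data sets. Its mean SE was 0.13–0.22. When the model was calibrated it rejected in 1–4%.

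A second simulation used LP ~ N(−3, 2²) or N(−2, 1.5²), half of the LP variance between subjects, within-subject latent correlation of 0.3, and 400 runs per scenario. For true shifts of ±0.5 or ±1 logit, the slope test rejected in 5–7% of runs. The intercept test rejected in 98.5–99.5% of runs at ±0.5 and in 100% at ±1.

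**3. Non-rejection as evidence of calibration**

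| True slope | Not rejected, first simulation | Not rejected, second simulation |
|---|---|---|
| 0.9 | 13–77% | 58% |
| 0.8 | 0–24% | 4% |

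A true slope of 0.9 can therefore be labelled well calibrated often or seldom, depending on inputs that the plan does not have.

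**The case against.** The strongest reply is that calibration in level does not matter for what this study delivers. Every aim uses a binary call at a threshold fixed on the Training Data, and no predicted probability is used in any decision. If a shift in level came from a changed predictor distribution, it would show in sensitivity and specificity. If it came only from a changed AF prevalence, those measures would be unharmed. The slope test also suits the plan's main worry, overfitting after selection among 24 candidate basis functions. The wording is exploratory, and the fitted intercept and re-estimated coefficients would be there for the analyst to see.

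Much of this stands. No aim depends on calibration, the slope test is useful against overfitting, and the simulated percentages are illustrations. Doubled odds is an arbitrary shift, and symptom-triggered recordings beyond the 29 were left out.

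Three things do not stand.

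- The plan chooses to draw a calibration conclusion, so the rule behind it should be able to support one.
- The other planned output does not close the gap. ROC curves are also unchanged by a constant added to LP. Re-estimation moves all coefficients together and has no criterion, so it does not isolate a change in level. The intercept fitted alongside a free slope is the level at LP = 0; it is not the average error in level, and the plan does not mention it.
- The free intercept is inferred, not stated. If it were forced to zero, the slope test would react to a shift (89–100% rejection in the second simulation), but it would mix level with spread. Treating non-rejection as proof would remain wrong.

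**Conclusion.** The concern holds. As written, the calibration rule cannot detect uniform over- or under-prediction on the logit scale, and it treats a large p-value as evidence of good calibration. The first part is algebraic and needs only the default free intercept. The second holds whatever the intercept. The simulated sizes (8.6% predicted against 5.8% observed; 27.9% against 21.7%) show what a doubling of the odds would look like under the assumed AF burden, clustering and predictor distribution. They are not forecasts for this trial.

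The effect is confined to the secondary calibration conclusion. The estimates and tests of sensitivity and specificity at the locked threshold are unaffected, and the slope test keeps its value as a check on overfitting.

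**What to change.** In section 8.2, replace the reading of the slope = 1 test by the following, before the Validation Data are opened:

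- Report the calibration intercept, from a logistic model with the linear predictor as offset (slope fixed at 1), with a subject-clustered robust confidence interval.
- Report the calibration slope with the same type of interval.
- Optionally, add a joint test of intercept = 0 and slope = 1.
- Delete the parenthesis in "with a large p-value (indicating good calibration") and base the calibration conclusion on the two intervals.

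This follows the preference for estimates and intervals over tests that the same section states for sensitivity and specificity. It costs about one sentence in the plan and a few lines of output from data already collected, with no added patients or recordings.

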**-AIM3: Time delay in AF detection:**

We will estimate the sensitivity of the resulting technique as a function of the elapsed time  $t$  since initiation of AF, which is fundamentally different from the instantaneous sensitivity targeted in Aims 1-2. Since the time of AF will fall randomly within the monitoring period for the ~50 AF patients (half of the estimated ~95 ERAF in Table 1), this will induce right-censoring of the time from first onset of AF (as detected via ECG) until the first true AF detection by VPG, as some patients will only have 1 day of post-AF follow-up while others might have 10 days of post-AF follow-up. Thus, the Kaplan-Meier estimator will be used to estimate sensitivity( $t$ ), and pointwise confidence bounds will be based on Greenwood's formula for the variance. It should be noted that patients can move out of and possibly back into AF (as measured by ECG) repeatedly over time. If VPG falsely detects AF while the patient is in sinus rhythm (according to ECG), such false detection of AF by VPG will not be counted (see Figure 7). Only true AF detection by VPG, when the patient is in AF (as measured by ECG), will meet the endpoint definition. Thus, if a patient were to quickly resolve from initial AF to sinus rhythm then the sensitivity of the VPG monitoring process would be penalized as it will be impossible to detect AF in such a patient via intermittent monitoring, unless s/he were to return to AF and be monitored during that subsequent episode. While sensitivity ( $t=48$  hours) is of particular interest, we will estimate the sensitivity curve for all  $t$  from 0 to up to 14 days, along with pointwise confidence limits. Similarly, we will use the Kaplan-Meier method to estimate the distribution of the time from hospital discharge (in sinus rhythm) until the first false AF detection by VPG. The latter curve will provide an estimated probability of false detection of AF as a function of follow-up time  $t$ , which can be interpreted as  $1 - \text{specificity}(t)$  of the VPG monitoring process. Note that once a patient enters AF (as measured by ECG), if VPG were to (correctly) detect AF then such true AF detection would not meet the endpoint definition, and false AF detection by VPG would be impossible until the patient returned to

sinus rhythm. Thus, this specificity( $t$ ) of the intermittent VPG monitoring process will be inflated by high prevalence and burden of AF, just as sensitivity( $t$ ) will be reduced by low AF burden. As an alternative characterization, we will censor patients at onset of AF (as measured by ECG) in order to obtain a pure estimate of sensitivity( $t$ ) during completely AF-free follow-up. For estimating sensitivity( $t$ ) we could similarly opt to censor patients as soon as they resolve to sinus rhythm, in order to get a pure estimate of sensitivity( $t$ ) during the first contiguous period of AF (as measured by ECG). However, we prefer the more conservative estimator of sensitivity( $t$ ) that penalizes the intermittent VPG monitoring system for failing to detect transient AF in a timely fashion, whereas we prefer the (also conservative) pure estimator of specificity( $t$ ) during completely AF-free follow-up.

### 8.3 Data and Safety Monitoring

On a monthly basis, the PI will routinely review cumulative data throughout the study to ensure subject safety and continued validity/scientific merit.

